5.1 General Considerations

- All study analyses will be conducted separately for Groups A and B, unless indicated otherwise.
- Considerations for type I error adjustment for conducting interim review(s) of the primary outcome:
 - o Group A:
 - For the estimated proportion difference between Arm 1 and Arm 3, if an interim look with a two-sided 99.9% confidence interval occurs to assess potential harm, the type I error (alpha) for the final analysis will not be adjusted. This is because 0.1% alpha spending in the interim look would have a minimal effect on the final confidence interval.
 - For the superiority comparison between Arm 2 and Arm 3, a repeated confidence interval approach using a Lan-DeMets spending function with O'Brien-Fleming type boundaries that accounts for the repeated analyses due to interim efficacy monitoring will be provided.

Group B:

- If an interim look with a 99.9% confidence interval occurs in Group B to assess potential harm, no adjustment will be made to the type I error (alpha) for the final analysis.
- Summaries of continuous variables will include mean with standard deviation, min, Q1, median, Q3, and max.
- For binary and categorical variables, estimated proportions will be provided.
- The data summaries will include the number or participants with data who are included in the analysis.
- Study visits corresponding to the protocol schedule of evaluations for the intended weeks will be used for the analysis, unless stated otherwise.
- In the event of multiple results within a window, the one closest to the targeted scheduled evaluation week will be used.
- Baseline refers to result closest to Week 0 prior to initiation of study vaccination.
- Calculated study visits will be used for laboratory measurements summarized or listed by week.
- No statistical comparisons across groups for baseline characteristics are planned for this randomized clinical trial.
- Any participant-level information will be identified by the masked participant identifier (Public ID).

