## 9. 5.5.2 Prohibited Medications

Clarification about COVID-19 administration was added as shown below:

HBV vaccine preparations other than study vaccines HEPLISAV-B and ENGERIX-B are prohibited. Standard-of-care (SOC) vaccines, including COVID-19 vaccines, will be permitted during the conduct of this study. If administration of a COVID-19 vaccine occurs after study entry and near the 2nd or 3rd study vaccine dose, adjust the 2nd or 3rd dose of the study vaccine to avoid immediate overlap reactogenicity; however, it is not prohibited to give them together, and this is at the discretion of the site investigator. If an SOC vaccine and/or COVID-19 vaccine is administered on the same day as the study-provided vaccine, use different arms. Refer to the A5379 PSWP for further details about COVID-19 vaccines and this study.

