2.3.2 Secondary Objectives

Group A

- 1. To compare the week 12 geometric mean titers (GMT) of a two-dose regimen of HEPLISAV-B (Arm 1) versus the week 28 GMT of a standard three-dose regimen of ENGERIX-B (Arm 3) in HBV vaccine-experienced participants living with HIV.
- To compare the week 28 GMT of a three-dose regimen of HEPLISAV-B (Arm 2) versus a standard three-dose regimen of ENGERIX-B (Arm 3) in HBV vaccine-experienced participants living with HIV.
- 3. To compare the SPR and GMT 4, 8, 24, and 48 weeks after last vaccination of a two-dose regimen of HEPLISAV-B (Arm 1) versus a standard three-dose regimen of ENGERIX-B (Arm 3) in HBV vaccine-experienced participants living with HIV.

- 4. To compare the SPR and GMT 8, 24, and 48 weeks after last vaccination of a three-dose regimen of HEPLISAV-B (Arm 2) versus a standard three-dose regimen of ENGERIX-B (Arm 3) in HBV vaccine-experienced participants living with HIV.
- 5. To compare the SPR and GMT 4, 8, 24 and 48 weeks after last vaccination of a two-dose regimen of HEPLISAV-B (Arm 1) versus a three-dose regimen of HEPLISAV-B (Arm 2) in HBV vaccine-experienced participants living with HIV.
- 6. To assess SPR and GMT at weeks 4, 8, 12, and 24 between HEPLISAV-B (Arms 1 and 2 combined) and ENGERIX-B (Arm 3) in HBV vaccine-experienced participants living with HIV (Group A).
- To describe incidence of Grade≥2 AEs within 4 weeks of each injection in each study arm.
- 8. To assess host characteristics associated with vaccine response.
- 9. To compare SPR and GMT at week 72 between HEPLISAV-B two-dose (Arm 1) and three-dose arms (Arm 2).

Group B

- 1. To determine the week 28 GMT of a three-dose regimen of HEPLISAV-B in HBV vaccine-naïve participants living with HIV.
- 2. To determine the SPR and GMT of a three-dose regimen of HEPLISAV-B at weeks 32, 48, and 72 in HBV vaccine-naïve participants living with HIV.
- 3. To determine the SPR and GMT of a three-dose regimen of HEPLISAV-B at weeks 4, 8, 12, and 24 in HBV vaccine-naïve participants living with HIV.
- 4. To describe incidence of Grade ≥2 AEs within 4 weeks of each injection.
- 5. To assess host characteristics associated with vaccine response.

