3.2 Secondary Outcome Measures

3.2.1 Group A

- 1. HBsAb titer at the following study visits in Arm 1:
 - a. Week 4 [Secondary Objective 6]
 - b. Week 8 [Secondary Objectives 3, 5, and 6]
 - c. Week 12 [Secondary Objectives 1, 3, 5, and 6]
 - d. Week 24 [Secondary Objective 6]
 - e. Week 28 [Secondary Objectives 3 and 5]
 - f. Week 52 [Secondary Objectives 3 and 5]
 - g. Week 72 [Secondary Objective 9]
- 2. SPR defined as HBsAb ≥10 mIU/mL at the following study visits in Arm 1:
 - a. Week 4 [Secondary Objective 6]
 - b. Week 8 [Secondary Objectives 3, 5, and 6]
 - c. Week 12 [Secondary Objectives 3, 5, and 6]
 - d. Week 24 [Secondary Objective 6]
 - e. Week 28 [Secondary Objectives 3 and 5]
 - f. Week 52 [Secondary Objectives 3 and 5]
 - g. Week 72 [Secondary Objective 9]
- 3. HBsAb titer at the following study visits in Arm 2:
 - a. Week 4 [Secondary Objective 6]
 - b. Week 8 [Secondary Objective 6]
 - c. Week 12 [Secondary Objective 6]
 - d. Week 24 [Secondary Objective 6]
 - e. Week 28 [Secondary Objectives 2 and 5]
 - f. Week 32 [Secondary Objectives 4 and 5]
 - g. Week 48 [Secondary Objectives 4 and 5]
 - h. Week 72 [Secondary Objectives 4, 5, and 9]
- 4. SPR defined as HBsAb ≥10 mIU/mL at the following study visits in Arm 2:
 - a. Week 4 [Secondary Objective 6]
 - b. Week 8 [Secondary Objective 6]
 - c. Week 12 [Secondary Objective 6]
 - d. Week 24 [Secondary Objective 6]
 - e. Week 28 [Secondary Objective 5]
 - f. Week 32 [Secondary Objectives 4 and 5]
 - g. Week 48 [Secondary Objectives 4 and 5]
 - h. Week 72 [Secondary Objectives 4, 5, and 9]
- 5. HBsAb titer at the following study visits in Arm 3:
 - a. Week 4 [Secondary Objective 6]
 - b. Week 8 [Secondary Objective 6]

- c. Week 12 [Secondary Objective 6]
- d. Week 24 [Secondary Objective 6]
- e. Week 28 [Secondary Objectives 1, 2 and 3]
- f. Week 32 [Secondary Objectives 3 and 4]
- g. Week 48 [Secondary Objectives 3 and 4]
- h. Week 72 [Secondary Objectives 3 and 4]
- 6. SPR defined as HBsAb ≥10 mIU/mL at the following study visits in Arm 3:
 - a. Week 8 [Secondary Objective 6]
 - b. Week 12 [Secondary Objective 6]
 - c. Week 24 [Secondary Objective 6]
 - d. Week 28 [Secondary Objective 3]
 - e. Week 32 [Secondary Objectives 3 and 4]
 - f. Week 48 [Secondary Objectives 3 and 4]
 - g. Week 72 [Secondary Objectives 3 and 4]
- 7. Grade ≥2 AEs within 4 weeks after each injection [Secondary Objective 7]

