4.2.2 Details on Outcome Measures for 4.1.1 - 4.1.3

- SPR at 12 weeks after the study randomization/registration for the 2-dose HEPLISAV-B vaccine series will be determined by antibody result at Week 12 study visit using the visit window specified in the protocol schedule of events. If the completion of vaccine series is delayed up to 4 weeks (as described in Protocol Version 2.0 Section 6.2.3 on Missed Vaccination Visits), then the subsequent antibody result within 8 weeks with an analogous visit window will be used.
- SPR at 28 weeks after the initiation of the 3-dose vaccine series (HEPLISAV-B or ENGERIX-B) will be determined by antibody result at Week 28 study visit using the visit window specified in the protocol schedule of events. If the completion of vaccine series is delayed up to 4 weeks (as described in Protocol Version 2.0 Section 6.2.3 on Missed Vaccination Visits), then the subsequent antibody result within 4 weeks with an analogous visit window will be used.

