4.6.2 Details on Outcome Measures for 4.5.1 – 4.5.5

- For HBsAb titer at 12 weeks after the initiation of the 2-dose series and for 28 weeks after
 the initiation of the 3-dose series (Secondary Estimands in Sections 4.5.1, 4.5.2 and
 4.5.5), antibody results corresponding to SPR measurements described in Section 4.2.2
 will be used.
- For HBsAb titer at 52 weeks after the initiation of the 2-dose series and 72 weeks after
 the initiation of the 3-dose series (Secondary Estimands in Sections 4.5.3 and 4.5.4),
 antibody results at Week 52 study visit and at Week 72 study visit, respectively, will be
 used.

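### Group A Secondary Objectives 3 and 5 (and the 8-week point of Objective 4) are timed from the last dose but analysed by study week, and the late-series rule misses the Arm 1 Week 8 and three-dose Week 32 results

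*SAP*

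**What the plan says.** **Objectives.** SAP 2.3.2 sets Objective 3 (Arm 1 against Arm 3) as "To compare the SPR and GMT 4, 8, 24, and 48 weeks after last vaccination of a two-dose" regimen against the control. Objective 5 uses the same four times for Arm 1 against Arm 2. Objective 4 (Arm 2 against Arm 3) reads "To compare the SPR and GMT 8, 24, and 48 weeks after last vaccination".

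**Outcome measures.** SAP 3.2.1 attaches these objectives to study visits: Weeks 8, 12, 28 and 52 in Arm 1, and Weeks 28, 32, 48 and 72 in Arms 2 and 3 (Objective 4 starts at Week 32). For example, the Arm 1 entry reads "Week 8 [Secondary Objectives 3, 5, and 6". SAP 5.1 makes the scheduled visit the default: "Study visits corresponding to the protocol schedule of evaluations for the intended weeks will be used for the analysis, unless stated otherwise".

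**Late series.** SAP 4.2.2 states another rule for the primary SPR only. "If the completion of vaccine series is delayed up to 4 weeks", a later sample is used: within 8 weeks for the two-dose series and within 4 weeks for the three-dose series. SAP 4.6.2 carries those samples over to the titers of 4.5.1, 4.5.2 and 4.5.5. For the 48-week estimands (4.5.3, 4.5.4) it uses "antibody results at Week 52 study visit and at Week 72 study visit, respectively", and those estimands count their weeks from the start of the series.

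**Delays are foreseen.** The estimand tables keep participants with a late series under a treatment policy strategy. Item 9 of the Letter of Amendment (Protocol 5.5.2) asks sites, when a COVID-19 vaccine falls near a later study dose, to "adjust the 2nd or 3rd dose of the study vaccine to avoid immediate overlap reactogenicity". It also leaves giving both together to the site investigator.

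**The concern.** Time since last dose and study week agree only when the last dose is on time. When it is late, the SAP corrects one of the two early post-series samples in each regimen, and not the same one. In Arm 1 the second sample (Week 12) has a rule and the first (Week 8) has none. In the three-dose arms the first (Week 28) has a rule and the second (Week 32) has none.

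This matters because the primary Arm 1 against Arm 3 contrast compares 8 weeks post-series with 4 weeks post-series (SAP 3.1.1). Objective 3 is where the two regimens are compared at equal times since the last dose. A one-dose sample counted as a two-dose response would make the two-dose regimen look weaker than it is in that comparison.

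**Working it through.** **Step 1: reproduce the SAP's labels.** Interval = visit week − week of last dose. The planned last dose is Week 4 in Arm 1 and Week 24 in Arms 2 and 3 (SAP 2.1.1).
- Arm 1: 8 − 4 = 4; 12 − 4 = 8; 28 − 4 = 24; 52 − 4 = 48.
- Arms 2 and 3: 28 − 24 = 4; 32 − 24 = 8; 48 − 24 = 24; 72 − 24 = 48.

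These match the objectives, and SAP 4.2.3 itself equates Week 8 with 4 weeks after the two-dose series.

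**Step 2: delay the last dose, with visits fixed to study entry.** Interval = label − delay, the same in both schedules.

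| Delay (weeks) | First visit, labelled 4 (Arm 1 Week 8; Arms 2/3 Week 28) | Second visit, labelled 8 (Arm 1 Week 12; Arms 2/3 Week 32) |
|---|---|---|
| 0 | 4 | 8 |
| 1 | 3 | 7 |
| 2 | 2 | 6 |
| 3 | 1 | 5 |
| 4 | 0 | 4 |
| Late-series rule exists? | Arm 1 no; Arms 2/3 yes | Arm 1 yes; Arms 2/3 no |

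At a 4-week delay dose 2 falls on about day 56, the nominal Week 8 day. With a ±7-day window (assumed for Arm 1; the Arms 2 and 3 schedule shows it), the Week 8 sample lies between 7 days before and 7 days after dose 2.

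**Step 3: consequences.**
- *4-week contrast (Objectives 3 and 5).* The SAP does not say whether these objectives reuse the re-anchored Week 28 result. If they do, a true 4-week three-dose value is set against an Arm 1 value taken 0 to 3 weeks after dose 2. If they do not, both sides carry early samples.
- *Double use.* With dose 3 at Week 28, the 4-week target is 28 + 4 = Week 32. That sample is also the scheduled 8-week result.
- *8-week contrast (Objectives 3 and 5).* The asymmetry reverses, but at delays of up to 4 weeks both samples nominally follow the last dose by at least 4 weeks.
- *Objective 4.* Both arms share one schedule, so the 8-week label can mean 4 to 7 weeks in either. This is mainly mislabelling.

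**Step 4: size, on assumed inputs.** Let d be the share of Arm 1 delayed about 3 to 4 weeks, D the SPR gain from the last dose, and L the log10 titer gain. None of these is in the documents.
- SPR understatement = d × D: from 0.05 × 0.20 = 0.010 to 0.15 × 0.40 = 0.060, i.e. 1 to 6 points.
- GMT multiplier = 10^(−d × L): from 10^(−0.05 × 0.5) = 0.94 to 10^(−0.15 × 1.0) = 0.71.
- Low case: 2% delayed, with SPR of 60% instead of 75%, gives 0.02 × 0.15 = 0.003, i.e. 0.3 points.

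This is the understatement in Arm 1 alone. It passes in full to the contrast only if the other arm is re-anchored; otherwise the two arms' errors partly offset.

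**Step 5: what re-anchoring could recover with fixed visits and ±7 days.**

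| Delay (weeks) | Arm 1 targets (4-, 8-week) | Usable visits | Arms 2/3 targets | Usable visits |
|---|---|---|---|---|
| 1 | Weeks 9, 13 | 8, 12 | Weeks 29, 33 | 28, 32 |
| 2 | Weeks 10, 14 | none | Weeks 30, 34 | none |
| 3 | Weeks 11, 15 | 12, none | Weeks 31, 35 | 32, none |
| 4 | Weeks 12, 16 | 12, none | Weeks 32, 36 | 32, none |

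**The case against.** **Visits may move with the dose.** Protocol 6.2.3, which SAP 4.2.2 cites for missed vaccination visits, is available here only as the Letter of Amendment's remote-visit addition. SAP 5.1 also refers to calculated study visits without defining them. A reader might infer that the late-series rule proves visits stay fixed, since otherwise it would not be needed. The documents do not support that step. With dose 2 at Week 8, 8 weeks later is Week 16, and the Arm 1 schedule (Weeks 4, 8, 12, 24, 28, 52, 72) has no such visit, so the Arm 1 clause reads more naturally if visits do move. This part of the objection stands: the mislabelling is conditional.

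**The 48-week results are a stated choice.** A reader might infer that every time point, including 48 weeks, is wrongly anchored. SAP 4.5.3 and 4.5.4 define those variables at Weeks 52 and 72 from initiation, with late series included under treatment policy. Preferring time since the actual last dose there would be a different estimand, not a correction. This stands.

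**Treatment policy covers the rest.** It does so only in part. As written, the strategy says who is included, not which sample represents them. The primary estimands use the same strategy and are still re-anchored.

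**Re-anchoring everything would lose data.** At a 4-week delay, Arm 1 would need Weeks 12, 16, 32 and 56, and the three-dose arms Weeks 32, 36, 52 and 76. Only Week 12 and Week 32 respectively are scheduled in those arms. Dropping values because of a post-randomisation event also strains the missing-completely-at-random assumption of SAP 4.2.3 and 4.6.3. This stands against a blanket rule.

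**Materiality.** The 4-week contrast is neither primary nor among the key secondary estimands of SAP 4.5. The Letter permits giving a COVID-19 vaccine together with a study dose, so it shows a possible source of delay, not a rate.

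**Conclusion.** The point holds in a limited form and should be settled before analysis. The objectives and the analysis use different clocks. No available text aligns them for Arm 1 Week 8 or three-dose Week 32, and the existing late-series rule could treat the two regimens differently in the 4-week contrast.

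A sample at or just after the last dose requires a delay of about 3 to 4 weeks; shorter delays give one 2 to 3 weeks after it. The primary SPR and Objectives 1 and 2 have their own rule and are not affected. A reader might take 1 to 6 SPR points as an estimated bias, but it is only a range over assumed delay rates and dose gains. With few late doses the effect is minor, and if Protocol 6.2.3 moves visits with the dose the Arm 1 problem shrinks or disappears.

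**What to change.** In SAP 5.2.2, for the 4- and 8-week time points of Objectives 3, 4 and 5:

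1. Apply the 4.2.2 late-series rule in the same way in all arms, and state whether Objectives 3 and 5 use the re-anchored Week 12 and Week 28 results.
2. Where the series was completed late, do not count a result drawn on or before the last dose received as post-series.
3. Do not use one sample for two time points.
4. Report the scheduled-visit analysis alongside, with the number of re-anchored and missing results by arm.
5. State whether visits move with a delayed dose under Protocol 6.2.3.

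Leave the 48-week estimands (4.5.3, 4.5.4) at Weeks 52 and 72, and label them as weeks from initiation.

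The cost is SAP wording and some programming; vaccine administration times are already to be reported (SAP Section 6, item 6b). The drawback is that a participant with a late series may be missing at one or both time points: under the fixed-visit assumption, at both after a 2-week delay and at the 8-week point after 3 or 4 weeks. That is why both versions should be shown.

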5.2 Analysis Approaches

5.2.1 Group A Primary:

- For each of the two primary objectives on vaccine response, the primary outcome measure on the SPR will be analyzed as a binary variable.
- A score-based approach similar to the Wilson method for a SPR proportion difference will be used to estimate a stratified confidence interval, known as Newcombe method (Yan

- and Su, 2010). Four strata will be defined by sex at birth and screening diabetes status, and the strata will use Mantel-Haenszel weights (Mantel and Haenszel. 1959).
- Non-inferiority comparison between Arms 1 and 3: For the final analysis, a two-sided 97.5% confidence interval will be provided for the estimated proportion difference between Arm 1 and Arm 3 (Arm 3 minus Arm 1). If the resulting confidence interval lies entirely below the non-inferiority margin of 10%, then non-inferiority of Arm 1 compared to Arm 3 (control) will be concluded. Superiority of Arm 1 compared to Arm 3 will be concluded if the confidence interval lies entirely below zero.
- Superiority comparison between Arms 2 and 3: For the final analysis, a two-sided 97.5% stratified confidence interval will be provided for the proportion difference between Arm 2 and Arm 3 (Arm 2 minus Arm 3). A repeated confidence interval approach according to the realized Lan and DeMets implementation of the O'Brien-Fleming sequential stopping boundary that accounts for the repeated analyses due to interim efficacy monitoring will be provided. If the resulting confidence interval lies entirely above zero, then superiority of Arm 2 compared to Arm 3 (control) will be concluded.
- To address the study objectives on safety, the proportion of participants with AEs will be summarized with a two-sided 95% confidence interval in each study arm using the Wilson method, across stratification factors.

5.2.2 Group A Secondary:

- The secondary analyses on SPR will be conducted using a two-sided type I error rate of 2.5% without further correction for multiple analyses. This type I error was chosen to provide confidence intervals of widths comparable to the primary outcome analyses.
- The secondary objectives on the SPR comparisons will be addressed using the following analysis approach. A two-sided 97.5% confidence interval around the difference in proportions will be calculated using the Newcombe method. These will also be stratified confidence intervals, similar to the primary analysis approach.
- For the secondary objectives on the analysis of the antibody titer as a continuous measure, two-sided type I error rate of 5% without correction for multiple analyses will be used. The geometric mean titer will be calculated for each analysis group (study arm or combined study arms, depending on the objective) and compared using a t-test. A two-sided 95% confidence interval around the difference in the geometric means will be calculated assuming t-distribution of log₁₀-transformed antibody titer. The confidence intervals will be provided across stratification factors and within stratum.
- o For the secondary objective (e.g. Objective 6) where Arms 1 and 2 are combined to compare to Arm 3 (control), the analysis will occur if the directions in the outcome differences between Arm 1 and Arm 3 and between Arm 2 and Arm 3 are the same. Otherwise, the analysis where Arms 1 and 2 are combined will not be interpretable.
- To address the objective on post-injection AEs, the proportion of participants with events will be summarized with a two-sided 95% confidence interval in each study arm using the Wilson method.
- Logistic regression models will be developed to assess host characteristic factors
 associated with vaccine response defined by the primary outcome on the SPR. The
 factors include age, sex, race, diabetes, body mass index (BMI), CD4+ T-cell count, and
 smoking status at baseline. Each factor will be considered in a separate model that only

controls for the study arm as a covariate, and a p-value <0.20 will determine entry into a full model. Then all-subsets variable selection approach will be used with a p-value cutoff of 0.05 as a criterion to retain in the final model, while keeping the study arm in the model throughout the procedure.

5.2.3 Group B Primary:

- The primary outcome on the SPR at 4 weeks after the vaccination series will be assessed by estimating the proportion of participants who achieve SPR. A two-sided 95% confidence interval around the observed SPR proportion will be provided using the Wilson score method for binomial variables. If the confidence interval lies above 55%, then it will be concluded that the SPR proportion is greater than 55%.
- To address the primary objective on safety, the proportion of participants with AEs will be summarized with a two-sided 95% confidence interval using the Wilson method.

5.2.4 Group B Secondary:

- Each secondary analysis will be conducted using a two-sided type I error rate of 5% without correction for multiple analyses.
- To address the secondary objectives on the SPR at additional study weeks, a two-sided 95% confidence interval around the observed SPR proportion will be provided for each, using the Wilson score method for binomial variables.
- To address the secondary objectives related to antibody titer as a continuous measure, the GMT will be calculated with two-sided 95% confidence intervals, assuming tdistribution of log₁₀-transformed antibody titer.
- To address the study objective on post-injection AEs, the proportion of participants with events will be summarized with a two-sided 95% confidence interval using the Wilson method.
- Logistic regression models will be developed to assess host characteristic factors associated with vaccine response defined by the primary outcome on the SPR. The approach described for Group A (Section 5.2.2 above) will also be used for Group B.

References:

Yan, X., & Su, X. G. (2010). Stratified Wilson and Newcombe confidence intervals for multiple binomial proportions. Statistics in Biopharmaceutical Research, 2(3), 329-335.

Mantel, N., and Haenszel, W. (1959). "Statistical Aspects of Analysis of Data from Retrospective Studies of Disease." Journal of the National Cancer Institute 22:719–748.

6 Report Contents

Additional details will be provided in an AIP. In addition to results for primary and secondary outcome measures, baseline characteristics and study status are reported to ClinicalTrials.gov.

- 1. CONSORT Diagram
- 2. Study history
 - a. A summary of changes to and clarifications of the protocol
 - b. A brief summary of the DSMB reviews
- Study entry
 - a. Screening: Number of participants screened for the study
 - b. Accrual: Tables of accrual by month and by site
- 4. Baseline characteristics
 - a. Demographics: age, sex, gender, IV drug use, race, ethnicity, country
 - b. Weight and BMI
 - c. Plasma HIV-1 RNA level, CD4+ and CD8+ T-cell count and percent
 - d. ARV regimen
 - e. Smoking status
 - f. Diabetes status
- 5. Study status
 - a. Listing of premature study discontinuation with reasons. For premature discontinuations, the number of weeks on study will be provided.
- 6. Study treatment status
 - a. Listing of premature discontinuations of vaccination series with reasons. For premature discontinuations, the number of vaccines received will be provided.
 - b. Number and times of administered vaccines
- 7. Adverse events and deaths
 - a. Summary of all reportable AEs defined in Section 7.2 of the protocol by MedDRA system organ class (SOC) and preferred term (PT) and by grade.
 - b. Summary of the participants who died, including primary cause of death with weeks from study entry.
 - c. Listing and narratives of deaths.
- 8. Pregnancies
 - a. Listing and description of all available information related to pregnancy and outcome.
- 9. HIV-Related Summaries
 - a. CD4 cell count and changes from baseline at study visits
 - b. HIV-1 RNA at study visits
- 10. Analysis of Primary Outcome Measures

Group A Outcomes Described in Section 3.1.1:

a. Primary Objective 1 described in Section 2.3.1 will be addressed by estimating the difference between Arms 1 and 3 (Arm 3 minus Arm 1) in the proportions of participants who achieve SPR, using the approach described in Section 5.2.1.

- b. Primary Objective 2 described in Section 2.3.1 will be addressed by estimating the difference between Arms 2 and 3 (Arm 2 minus Arm 3) in the proportions of participants who achieve SPR, using the approach described in Section 5.2.1.
- c. Primary Objective 3 described in in Section 2.3.1 will be addressed by estimating the proportion of participants with reported AEs, using the approach described in Section 5.2.1.

Group B Outcomes Described in Section 3.1.2:

- a. Primary Objective 1 described in Section 2.3.1 will be addressed by estimating the SPR proportion, using the approach described in Section 5.2.3.
- b. Primary Objective 2 described in Section 2.3.1 will be addressed by estimating the proportion of participants with reported AEs, using the approach described in Section 5.2.1. In addition, descriptive tables summarizing the events and the number of participants experiencing the events will be provided by grade. For the descriptive tables, the worst graded event per participant over time will be used.

11. Analysis of Secondary Outcome Measures

Group A Outcomes Described in Section 3.2.1:

- a. Secondary Objectives 1, 2, 3, 4, 5, 6, and 9 from Section 2.3.2 related to GMT will be addressed by estimating the difference in GMT between study arms (or between Arm 3 and the combined Arms 1 and 2 for Secondary Objective 6), using the approach described in Section 5.2.2. In addition, the geometric mean titer will be calculated for each study arm and compared using a t-test, as described in Section 5.2.2.
- b. Secondary Objectives 3, 4, 5 and 6 from Section 2.3.2 related to SPR will be addressed by estimating the SPR proportion differences between study arms (or between Arm 3 and the combined Arms 1 and 2 for Secondary Objective 6), using the approach described in Section 5.2.2.
- c. Secondary Objective 7 from Section 2.3.2 will be addressed by estimating the proportion of participants with post-injection AEs, using the approach described in Section 5.2.2. In addition, descriptive tables summarizing the events and the number of participants experiencing the events will be provided.
- d. Secondary Objective 8 from Section 2.3.2 will be addressed by logistic regression models described in Section 5.2.2.
- e. To assess the effect of sex and race on the vaccine response (per NIH guidance on reporting analyses of sex and racial differences in intervention effects for NIH-defined Phase III clinical trials), proportions of subgroups defined by sex and race who achieve the primary outcome will be estimated with confidence intervals, using the approach described in Section 5.2.2. In addition, note that logistic regression models for the primary outcome will include sex and race, and reported as secondary analyses.

Group B Outcomes Described in Section 3.2.2:

a. Secondary Objectives 1, 2 and 3 from Section 2.3.2 related to GMT will be addressed by estimating the GMT, using the approach described in Section 5.2.4.

- b. Secondary Objectives 2 and 3 from Section 2.3.2 related to SPR will be addressed by estimating the SPR proportion, using the approach described in Section 5.2.4.
- c. Secondary Objective 7 from Section 2.3.2 will be addressed by estimating the proportion of participants with post-injection AEs, using the approach described in Section 5.2.4. In addition, descriptive tables summarizing the events and the number of participants experiencing the events will be provided..
- d. Secondary Objective 8 from Section 2.3.2 will be addressed by logistic regression models described in Section 5.2.4. Note that logistic regression models for the primary outcome will include sex and race.

12. Intercurrent Events

Summaries of the number and timing of each intercurrent event in each treatment group will accompany each analysis where intercurrent events are specified in Section 4.

13. Supplementary Analyses of Primary Outcome Measures

The following analyses restricted to participants who complete the vaccine series as prescribed will be conducted.

Group A SPR Outcomes Described in Section 3.1.1:

- a. Primary Objective 1 described in Section 2.3.1 will be addressed in the subset by estimating the difference between Arms 1 and 3 (Arm 3 minus Arm 1) in the proportions of participants who achieve SPR, using the approach described in Section 5.2.1.
- b. Primary Objective 2 described in Section 2.3.1 will be addressed in the subset by estimating the difference between Arms 2 and 3 (Arm 2 minus Arm 3) in the proportions of participants who achieve SPR, using the approach described in Section 5.2.1.

Group A Outcomes Described in Section 3.2.1:

a. Secondary Objectives 1 and 2 from Section 2.3.2 related to GMT will be addressed in the subset by estimating the difference in GMT between study arms, using the approach described in Section 5.2.2. In addition, the GMT will be calculated for each study arm and compared using a t-test, as described in Section 5.2.2.

Group B SPR Outcomes Described in Section 3.1.2:

a. Primary Objective 1 described in Section 2.3.1 will be addressed in the subset by estimating the SPR proportion, using the approach described in Section 5.2.3.

Group B Outcomes Described in Section 3.2.2:

a. Secondary Objective 1 from Section 2.3.2 related to GMT will be addressed in the subset by estimating the GMT, using the approach described in Section 5.2.4.
